General Analytic Strategies. We will examine all variables to determine if parametric distributional assumptions are valid (e.g., normality for the continuous variables). Variables not meeting approximate distributional assumptions will either be transformed or modeled using nonparametric methods. In addition, we will explore the variability and correlation structure of the CHD outcome variables and PTSD symptom severity. Evidence of imbalance in baseline demographic (age, gender, veteran/civilian status) or clinical (high blood pressure, diabetes, major depression) characteristics will be noted and discussed as to whether they are clinically significant and we will consider sensitivity analyses including these covariates in models (models described below separately for each aim), as recommended by the Committee for Proprietary Medicinal Products guidelines (Committee for Proprietary Medicinal Products, 2004). We will also minimize the imbalance on variables known to be related to the predictor and outcome variables by stratifying randomization by gender, age, and major depressive disorder. As the main goal of the aims for this study is to understand how changes in PTSD symptom severity impact changes in CHD markers, we will conduct both an intent-to-treat analysis where participants will be analyzed as part of the group to which they are randomized, regardless of intervention adherence, and a per-protocol or as-treated analysis to strengthen the evidence that the mechanism for the effects of CPT-C vs. control on CHD markers is through PTSD symptom severity changes.

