stratification variables of gender, age, and comorbid major depressive disorder (Committee for Proprietary Medicinal Products, 2004) and as identified in the detailed description of methodologies and in the general analytic section, sensitivity analysis will also include the potential important covariates of functional comorbidity, smoking status, substance abuse, and habitual physical activity. Our main analysis technique for the primary outcome, general linear models via maximum likelihood estimation, uses all available data on subjects, rather than using only subjects with completely observed information, implicitly accommodating missingess when related to prior outcome, or to other baseline covariates included in the model (defined as missing at random).

Aim 2: To examine mechanisms of change in CHD risk biomarker outcomes in a mediation framework. It has been repeatedly demonstrated that individuals suffering from PTSD show excessive SNS, reduced PNS activity, chronic inflammation, and endothelial dysfunction and a number of studies have presented evidence suggestive of the possibility that these CHD markers of risk may be normalized following PTSD treatment (Cohen et al., 2000; Nishith et al., 2003; Blanchard et al.2002; Rabe et al., 2006; Hinton, Hofmann, Pollack, & Otto, 2009). The objective of this aim is to examine whether the change in PTSD symptoms explains the change in CHD biomarkers observed following CPT-C. To achieve this objective, we will test the working hypothesis that improvements in CHD risk biomarkers will be mediated by reductions in PTSD symptom severity. These findings will help establish whether PTSD symptoms themselves are determinants of CHD risk, independently of psychiatric comorbidity and health behaviors associated with cardiovascular risk. When the proposed studies for aim #2 have been completed, it is our expectation that the magnitude of the contribution of PTSD symptom load towards each of the evaluated CHD risk biomarkers will be clarified. Such a finding would be of importance, because it would provide support for a direct role of PTSD symptoms in the CHD risk observed in PTSD and would also identify which cardiac biomarker would provide the most utility in screening and CHD risk stratification in order to predict and prevent the onset of CHD.

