treatment group: $C = \gamma_0 + \gamma_1^*$ treatment. We then fit a model examining the relationship between the mediator and post-treatment change in CHD biomarkers (Y): Y = β_0 + treatment* β_1 + C* β_2 . Finally, to show mediation, we will test that the product of γ_1 and β_2 is not equal to 0 using an extension of the Sobel first-order test (Fritz & MacKinnon, 2007); that is, the the effects of CPT-C on CHD risk biomarkers are attributable to its effects on PTSD symptom improvement. To fully understand these relationships, we will also investigate the MacArthur approach, where our second model will be (Y): Y = β_0 + treatment* β_1 + C* β_2 + C* treatment * β_3 . Under this approach, improvements in CHD biomarkers are attributable to improvements in PTSD symptoms if there is evidence that γ_1 is not equal to 0, and either β_2 or β_3 are not equal to zero. The model will also be adjusted for stratification variables of gender, age, and major depressive disorder, and as detailed above in the general analytic section in the sensitivity analysis, we will evaluate and include other potentially important covariates, including change in anxiety and depressive symptoms estimated from the changes in HADS anxiety and depression following the intervention. We will also explore an as-treated analysis to maximize the potential mediation effects of PTSD symptom severity changes over time. For these analyses, data will be deemed usable for any individual who drops out of the study after two weeks or more of CPT-C or WP-CON, if PTSD symptom change is available and a repeat CHD biomarker assessment can be performed after the PTSD symptom change is assessed.

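### Aim 3 lists no treatment main effect, so any CPT-C effect that bypasses PTSD change would load on its slopes; secondarily, Aim 2 names neither baseline

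*Combined protocol and SAP*

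**What the plan says.** **Aim 2, Analytic strategy.** The mediator C is PTSD change from week 0 to week 6; the outcome Y is biomarker change, determined at week 7. C is regressed on treatment. Then "We then fit a model examining the relationship between the mediator and post-treatment change in CHD biomarkers (Y": the regressors are treatment and C, and the MacArthur version adds their product. "The model will also be adjusted for stratification variables of gender, age, and major depressive disorder". For sensitivity, "we will evaluate and include other potentially important covariates, including change in anxiety and depressive symptoms", the change being measured by the HADS. That clause is open-ended, but HADS change is its only example. It refers back to General Analytic Strategies, which lists "baseline demographic (age, gender, veteran/civilian status) or clinical (high blood pressure, diabetes, major depression) characteristics". Aim 1 adds functional comorbidity, smoking, substance abuse and physical activity. None of these lists names baseline PCL-5 or baseline biomarker.

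**Aim 3, Analytic strategy.** The listed predictors are PTSD change and an interaction with gender or major depressive disorder. The word *arm* sits unexplained inside the name of that interaction. Baseline demographic and clinical covariates are added but not itemised. No treatment main effect is listed. The output is 95% confidence intervals by gender and depression status.

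**Use of the results.** General Analytic Strategies says: "As the main goal of the aims for this study is to understand how changes in PTSD symptom severity impact changes in CHD markers". Aim 2 states: "The objective of this aim is to examine whether the change in PTSD symptoms explains the change in CHD biomarkers observed following CPT-C", and adds "These findings will help establish whether PTSD symptoms themselves are determinants of CHD risk".

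**The concern.** Treatment moves PTSD symptoms and may also move biomarkers by other routes. The plan allows for this: the section on medications, health risk behaviors and psychosocial assessments will examine whether HADS anxiety or depression change mediates the CPT-C effect. Aim 2 holds such routes apart through its treatment coefficient β₁. Aim 3 has nowhere to put them except the PTSD-change slope. The error runs in the hypothesised direction, because a therapy that lowers PTSD scores and separately raises HRV makes PTSD reduction look beneficial for HRV. The stray *arm* also leaves an analyst unsure which interaction to fit.

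The second issue is β₂, the PTSD-change coefficient. Randomization protects γ₁, the treatment effect on PTSD change, but not β₂. Change-on-change is right if the PTSD–biomarker link is a stable trait. It is biased if correlated baseline deviations are not carried forward to follow-up. Adjusting for baselines reverses the problem. The documents give no ground for choosing between these cases, and no named analysis shows whether the conclusion depends on the choice.

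**Working it through.** **Inputs from the plan.** 120 randomized 2:1 with 20% attrition gives 120 × 0.8 = 96 completers (64:32). The baseline-to-follow-up correlation ρ is 0.3 to 0.6 (Power Analysis, for HRV). The largest effect in Table 2 is 0.60.

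**Assumed, not in the documents.** CPT-C lowers PTSD by a = 0.8 SD. A CPT-C effect d = 0.3 to 0.6 SD on the biomarker bypasses PTSD (0.6 is an upper bound, being Table 2's largest value). PTSD has the same ρ as HRV. The baseline PTSD–biomarker correlation r is 0 to −0.3. Stratification covariates are omitted.

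**Plan's nearest figure.** Detectable effect = (1.960 + 0.842) × √(1/64 + 1/32) × √(1 − 0.3²) = 0.579. Table 2 gives 0.60, which agrees after rounding to steps of 0.05. This confirms that 96 completers underlie the table. The point itself rests on no stated figure.

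**Terms listed in the text.**

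| Term | Aim 2 outcome model | Aim 3 model |
|---|---|---|
| PTSD change | yes | yes |
| Treatment main effect | yes | no |
| Interaction | PTSD change × treatment (MacArthur only) | PTSD change × moderator, with a stray *arm* |
| Baseline PCL-5, baseline biomarker | not named | not named |

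**Aim 3 slope, no true PTSD effect, r = 0.** With p = 2/3 allocated to CPT-C, p(1 − p) = 2/9. The within-arm variance of PTSD change is 2(1 − ρ). Without a treatment term the slope converges to −a·d·(2/9) / [2(1 − ρ) + a²·(2/9)].

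- ρ = 0.3, d = 0.3: −0.0533 / (1.4 + 0.1422) = −0.035; at d = 0.6, −0.069.
- ρ = 0.6, d = 0.3: −0.0533 / (0.8 + 0.1422) = −0.057; at d = 0.6, −0.113.

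Simulated false rejection of the pooled slope (20,000 replicates):

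| ρ | d = 0.3 | d = 0.6 |
|---|---|---|
| 0.3 | 6.6% | 10.9% |
| 0.5 | 7.8% | 15.7% |
| 0.6 | 9.1% | 20.0% |

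With arm and arm-by-moderator the rate is 4.6–5.3%. The interaction test rejects in 4.7–5.3% even without arm. The result depends on a: at a = 1 SD the range is 7–13% (ρ = 0.3) and 10–26% (ρ = 0.6).

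Suppose PTSD improves more in women, as Aim 3 expects (sizes assumed: 0.4 SD in men, 1.2 SD in women), and the bypass effect is equal. The women's 95% interval then misses the true slope in 7–9% (d = 0.3) or 10–19% (d = 0.6), the men's in 5–7%, and the interaction test rejects in 5–7%.

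**What arm does not repair.** If baseline deviations are correlated and not carried forward, β₂ converges to (1 − ρ)r/2. At ρ = 0.3, r = −0.3 that is 0.7 × (−0.3)/2 = −0.105. In that case the Aim 3 slope with both arm terms still rejects in about 16% (ρ = 0.3) or 8–9% (ρ = 0.6). It returns to about 5% only when both baselines are also included.

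**Aim 2, no true mediator effect, r = −0.1 to −0.3** (first-order Sobel test, since the plan does not define its extension):

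| | Not carried forward | Stable trait |
|---|---|---|
| Planned β₂ test | 5–18% | about 5% |
| Planned Sobel | 2.2–6.6% | 1.3–2.8% |
| Sobel with only γ₁ baseline-adjusted | 3.1–10.0% | 2.1–3.4% |
| β₂ adjusted for both baselines | about 5% | 6–44% |
| Sobel, both parts adjusted | not above 5% | 3.5–29.4% |

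Adjusting γ₁ for baseline PCL-5 cuts its standard error by 10–19%, close to the factor √((1 + ρ)/2). Used alone, it makes a biased β₂ more likely to pass the product test.

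**The case against.** The strongest reply is that the planned decision rules hold up. Aim 2 is decided by the product test, whose false rejection exceeds 5% only at the most extreme assumed correlation (r = −0.3). That r would have to remain after adjustment for gender, age and depression, in a sample all of whom score at least 25 on the CAPS. The MacArthur rule ("Under this approach, improvements in CHD biomarkers are attributable to improvements in PTSD symptoms if there is evidence that" γ₁ is non-zero and either β₂ or β₃ is) rejects in 7–10% with 0/1 coding, but already in about 7–8% at r = 0, so most of that excess is not a baseline matter. All of this stands.

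For Aim 3, the planned intervals are worded as a difference by gender and depression status. Read as the between-group contrast, they are almost untouched. That also stands, and limits the harm to the slopes themselves, pooled or within group. The moderator main effect is arguably present already, since gender and major depression appear in General Analytic Strategies under the same demographic and clinical labels. The stray *arm* could be read as an arm interaction, so the accurate statement is that no treatment *main effect* is listed. The baselines are unnamed, not ruled out.

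What the reply does not answer is why Aim 3 drops a term that Aim 2 carries for the same outcome. Treatment is not a baseline characteristic, so the covariate clause does not supply it.

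**Conclusion.** The omission in Aim 3 is plain from the text. Its effect is modest and conditional: a slope shift of 0.03 to 0.11 and false rejection of about 6 to 20%, given a bypass effect of 0.3 to 0.6 SD, a = 0.8 SD and r = 0. With no bypass effect, the missing arm term does no harm. The baseline point in Aim 2 is secondary. Its size depends on a correlation the documents do not give, and it is nil at r = 0 or under a stable trait.

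A reader might infer more than this. The documents do not support concluding that:

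- the Sobel test or the Aim 3 interaction test fails;
- the change-score model is wrong and should be replaced, since it fits the stated question;
- adding arm secures 5% error in general, since it removes only the bypass bias;
- a larger direct CPT-C effect is expected in women, since Aim 3 attributes their larger gains to larger PTSD improvement.

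Aim 1 and the sample size are unaffected, and Aim 3 is labelled exploratory. This is a minor-to-moderate improvement.

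**What to change.** 1. **Aim 3.** State that the interaction is PTSD change by moderator and remove or explain *arm*. Add treatment arm and arm-by-moderator, and list the moderator main effect explicitly. The cost is 2 degrees of freedom for the arm terms and standard errors 3–11% larger (pooled slope from 0.096–0.102 to 0.106; interaction from 0.191–0.205 to 0.212). An interaction with 80% power would have about 71–78%.
2. **Aim 2.** Keep the change-score models as primary. Pre-specify one companion that adds baseline PCL-5 and baseline biomarker, and do the same for the Aim 3 slopes. If the two disagree, describe the result as assumption-dependent. A positive companion alone is not a mediation finding.
3. **γ₁.** Put any baseline adjustment of γ₁ in the companion only, not in the primary product test.

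The companion costs SAP wording, one extra fit per biomarker per aim and a few degrees of freedom out of 96, using data already collected. In the not-carried-forward case it would mark about 64–90% of false Sobel results as assumption-dependent. At a true β₂ of −0.3 it would also mark some true results: 14–27% in that case and 0.2–7% under a stable trait (estimated with γ₁ adjusted in both versions).

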Approach. This RCT with repeated measurements of PTSD symptoms and CHD markers will provide a mechanism to evaluate the temporal relationship between the change in PTSD symptoms and the changes in ANS control mechanisms, endothelial function and inflammation. Using this temporal relationship, we will examine whether changes in PTSD symptoms mediate the effects of CPT-C on CHD markers.

Expected Results. We anticipate that the change in PTSD symptoms will mediate the relationship between CPT-C and CHD marker change, thereby identifying the role of reduction in PTSD symptoms as a mechanism for the improvement in CHD risk.

Analytic strategy. We propose to conduct mediation analyses using the more commonly known Baron and Kenny approach (Baron & Kenny, 1986) as well as the newer MacArthur approach (Kraemer, Kieser, Essex, & Kupler, 2008). By the MacArthur definition, the potential mediator must be during or post-treatment; therefore, the change in PTSD symptoms severity between week 0 and week 6 will be considered as a potential mediator. The outcome then will be participants' post-treatment change in CHD risk biomarkers, which will be determined at week 7. We will also explore the role of trajectories of change in PTSD symptom severity as a mediator of the post-treatment change in CHD risk biomarkers by deriving an individual-level summary measure of PTSD symptom change using the successive PTSD symptoms assessed at two week intervals. We will first fit a model to examine the relationship between the mediator (C) (i.e., change in PTSD symptoms during treatment) and

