0.50	40	0.55	22.0
0.50	50	0.55	27.5
0.60	40	0.50	20.0
0.60	50	0.50	25.0

assumed a range of correlations between 0.3 and 0.6 and standard deviations (SD) of 40 and 50. **Table 2** presents effect size differences with 120 subjects. Using the most conservative assumptions, with 80% power, alpha=0.05, SD=50, rho=0.3, and 20% attrition rate by 7-weeks we can detect an effect size difference of 0.60 (Cohen, 1988), corresponding to a difference of 30 units in mean HRV levels at 7-weeks between CPT-C and control. For the AIM 2 mediation analysis, we will test that the effect of CPT-

C on CHD biomarkers is attributable to changes in PTSD severity. We determined detectable effect sizes for mediation based on empirical power estimates for the product-of-coefficient test (i.e., the product of γ_1 and β_2) given by Fritz and MacKinnon (2007). With 120 subjects and a type-I error of 0.05, we will have 80% power to detect medium to large effect size differences for each of the parameters individually (e.g, γ_1 and β_2) that are part of the product test.

Missing Data. Our plans for preventing and dealing with missing data follow the guidelines set forth by the National Research Council's Panel on Handling Missing Data in Clinical Trials. First, , we have numerous strategies in place to prevent attrition; based on prior experience with a similar design and population, we anticipate that we will have less than 20% attrition. Second, as recommended by the panel, we will conduct two general types of sensitivity analyses for our primary analysis. If the missing values are related to measured factors, such as treatment group or baseline comorbidities, then multiple imputation will be used to incorporate information for these auxiliary variables while still preserving a parsimonious main treatment effect model (Collins, Schafer, & Kam, 2001). As a first sensitivity analysis, we will construct a general, multivariate imputation model using all observed CHD markers, treatment group, and any covariates predictive of missingness (Olsen, Stechuchak, Edinger, Ulmer, & Woolson, 2012). The primary analysis models will then be fit to the multiply imputed data and the estimates and standard errors will be combined using appropriate combining rules. We acknowledge the possibility that data may be missing not at random and propose as a second sensitivity analysis to explore pattern-mixture models and the toolkit of methods recently advocated by O'Kelly and Ratitch (2014).

References

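### Aim 2 does not state the reference distribution for its Sobel-type test of the indirect effect; if it is normal, the test is conservative at 96 to 120 participants and loses power that a product or bootstrap interval would keep

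*Combined protocol and SAP*

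**What the plan says.** The Analytic strategy under Aim 2 fits two regressions: PTSD change (C) on treatment, giving γ1, and biomarker change (Y) on treatment and C, giving β2. The deciding step is stated in one clause, a test that the product of γ1 and β2 "is not equal to 0 using an extension of the Sobel first-order test". A paper on sample size for mediated effects is cited, but the word extension is not explained.

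The same section adds the MacArthur approach, which puts a C-by-treatment term (β3) into the outcome model. It attributes biomarker improvement to PTSD improvement "if there is evidence that γ_1 is not equal to 0, and either β_2 or β_3 are not equal to zero". No treatment coding is stated, and nothing says which approach prevails if they disagree.

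Power Analysis says detectable effects for Aim 2 are "based on empirical power estimates for the product-of-coefficient test" and concludes: "With 120 subjects and a type-I error of 0.05, we will have 80% power to detect medium to large effect size differences" on each path. It gives no numeric path size. The 20% attrition used for the HRV calculation is not carried into this sentence.

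**The concern.** A first-order Sobel test divides γ1 × β2 by a first-order standard error and compares the ratio with a normal distribution. The product of two estimates is skewed and heavy-tailed unless both paths are strong relative to their standard errors, so the normal cut-off is too strict. A real mediated effect is then more likely to be missed.

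This matters because the Overview of the Study Approach makes the effect of PTSD change on biomarker change the main goal of the trial. The loss would also be avoidable: an interval that respects the shape of the product uses the same two regressions.

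**Working it through.** **Inputs from the documents.** 120 randomised 2:1 (80 and 40); 20% attrition by week 7, so 0.8 × 120 = 96 analysed (64 and 32); α = 0.05; two-sided, because the test is of inequality to zero; the two regressions above.

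**Assumptions, because the documents give no values.** γ1 from 0 to 1.2 residual SD; β2 from 0 to about 0.6; residual SD 1 in both models; normal errors; no direct effect; no covariates.

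**The plan's own figure.** The Aim 2 power statement is qualitative, so it can only be checked for plausibility. In simulation with 120 participants, the plain Sobel test has 74.7% power when both standardised paths are 0.32 and 83.0% when both are 0.34. It therefore reaches 80% at about 0.33, or γ1 ≈ 0.33/√(2/9) = 0.70 SD. That fits medium to large. At those two settings:

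- With 120, the Monte Carlo interval has 86.8% and 90.6% power, so the Sobel loss is 12.1 and 7.6 points.
- With 96, Sobel power is 57.1% and 66.9%, against 75.6% and 79.4% for the Monte Carlo interval.

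**Why the normal reference is strict.** Write z_a = γ1/SE(γ1) and z_b = β2/SE(β2). The first-order Sobel statistic is

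z = z_a·z_b / √(z_a² + z_b²),

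which is always smaller than the weaker of the two. With 96 analysed:

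- SE(γ1) = √(1/64 + 1/32) = 0.2165 and SE(β2) ≈ 1/√94 = 0.103.
- For γ1 = 0.65 and β2 = 0.30: z_a = 3.00, z_b = 2.91, so z = 3.00 × 2.91 / √(9.01 + 8.46) = 2.09. Two clearly significant paths give a borderline result.
- For β2 = 0 and γ1 = 0.80: z_a = 3.695. Rejection at 1.96 needs |z_b| > √[3.84 × 13.65 / (13.65 − 3.84)] = 2.31, a two-sided probability of 2.1%. Simulation also gives 2.1%.

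**False-positive rate of the Sobel test, β2 = 0 (simulated, 96 to 120 analysed).**

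| γ1 (SD) | Sobel |
|---|---|
| 0 | about 0% |
| 0.5 | 0.6–0.9% |
| 0.65 | 1.3–1.7% |
| 0.8 | 2.1–2.8% |
| 1.0 | 3.0–3.4% |
| 1.2 | 3.6–3.9% |

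The Monte Carlo interval gives 3.8–3.9% at 0.65 and 4.4–5.1% at 0.8.

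**Power (simulated).** Bootstrap figures are given where they were run.

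| N | γ1 | β2 | Sobel | Monte Carlo | Percentile bootstrap |
|---|---|---|---|---|---|
| 96 | 0.50 | 0.30 | 29.9% | 49.7% | 49.2% |
| 96 | 0.65 | 0.30 | 48% | 68% | – |
| 96 | 0.80 | 0.30 | 63.4% | 78.0% | 78.0% |
| 96 | 0.80 | 0.39 | 83.8% | 92.6% | 90.0% |
| 96 | 1.00 | 0.39 | 92.6% | 95.2% | – |
| 120 | 0.50 | 0.30 | 45.1% | 65.4% | 63.4% |
| 120 | 0.65 | 0.30 | 66% | 82% | – |
| 120 | 0.80 | 0.30 | 79.1% | 87.4% | 88.0% |
| 120 | 0.80 | 0.39 | 93.6% | 96.7% | 96.5% |
| 120 | 1.00 | 0.39 | 97.6% | 98.5% | – |

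The largest loss found was 21.6 points (46.7% against 68.3%), with 96 analysed and both standardised paths at 0.30. Monte Carlo power carries 2 to 3 points of simulation noise.

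**The MacArthur rule as written.** With 96 analysed, its power depends on how treatment is coded:

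- Coded 0/1 with control as 0: about 33% (0.65/0.30) and 38% (0.80/0.30). β2 is then the slope in the 32 controls alone.
- Coded ±0.5: about 64% and 74%.

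With β2 = 0 and γ1 of 0.65 to 0.80, its false-positive rate is about 6 to 10%, because either of two coefficients may qualify.

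**The case against.** The strongest objection is that the plan names an extension of the Sobel test, not the Sobel test. If the extension uses the distribution of the product, most of the loss goes. That stands, and it makes the point conditional. It does not remove it, because an analyst cannot tell from the text which method to run.

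Second, the plan has two criteria. A plain joint-significance rule (both paths significant) would match the Monte Carlo interval: 77.7% against 78.0% with 96 analysed at 0.80/0.30. But the MacArthur rule as written is not that rule. Its power turns on an unstated coding choice, and accepting either β2 or β3 has no multiplicity control.

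Third, a conservative test creates no false claims, and HRV under Aim 1 is the primary analysis. Both are true, and they limit the weight of the point.

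Three stronger readings are tempting and not supported:

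- A reader might infer one fixed error rate or power loss from the sample size. Both depend on path sizes that the plan does not give. The Aim 1 section also expects marked improvement in half of participants, so a large γ1, where the loss is small, is plausible.
- A reader might infer that the reported Aim 2 interval will be wrong. No interval is planned for Aim 2; confidence intervals are mentioned under Aim 3.
- A reader might infer that the mechanism question rests on the weak test alone. It does not, given the second criterion.

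**Conclusion.** The point holds in conditional form. The plan leaves the reference distribution of its deciding mediation test unstated. If that distribution is normal, then at 96 to 120 analysed the test runs at about 1 to 3% when β2 = 0 and γ1 is 0.5 to 0.8 SD. It gives up about 8 to 22 points of power for medium paths and about 3 to 9 for large ones, falling to about 1 point where power is already near 98%.

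These figures rest on the assumed paths, normal errors and no covariates. Where a plain Sobel test would have the plan's 80% power with 120, the loss is about 8 to 12 points. The change is worth making because it is cheap and bears on the trial's main mechanistic question. Aim 1 and its sample size are unaffected.

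**What to change.** In the Aim 2 Analytic strategy, replace the reference to an extension of the Sobel test with a named method: a two-sided 95% percentile-bootstrap interval for γ1 × β2, resampling within arm, or a Monte Carlo distribution-of-product interval. Conclude that there is an indirect effect if the interval excludes zero. Keep it two-sided, since the plan tests for a difference from zero in either direction. If the extension was meant to be a distribution-of-product method, saying so is enough.

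State that this interval decides Aim 2 and that the MacArthur analysis is supportive, and give the treatment coding for the latter. In Power Analysis, requote the Aim 2 power for the chosen method with numeric values for both paths and about 96 analysed.

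The cost is a few sentences of plan text, a few lines of code and a small amount of computing. No design or data-collection change is needed.
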